10.2 Safety Analysis

Safety analysis will be conducted on all patients who applied at least one dose of study product.

Adverse events will be classified using standard MedDRA terminology Version 19 or higher and summarized over all patients. Adverse events reported during the study will be tabulated in summary table listing by type, date of onset, date of resolution, incidence, severity, action taken, outcome and Investigator's opinion of relationship to the study product will be prepared. and symptoms of scalp psoriasis will not be considered adverse events, unless in the Investigator's opinion, they have increased in frequency and/or severity to such an extent that the Investigator/patient considers that it is in the patient's best interest to be dropped from continued participation in the study and given alternative therapy for their condition.

Concomitant medication use during the study will be tabulated by patient.

Ocular safety evaluations will be assessed at the discretion of the Investigator based on the findings of the HEENT exam performed at each visit along with the ocular discomfort reported by the patient. Ocular discomfort will be assessed by patients and reported to staff during clinic visits (Appendix C).

Adverse medical events experienced by the patients will be tabulated. The relationship of AEs, if any, to the study product will be assessed by the Investigator. Adverse events assessed as definite, probable, possible or not related to the study drug will be presented. Shift analysis using the categories, below, above and within the laboratory normal range will be performed to identify any specific laboratory parameter that shows a trend toward potentially clinically significant changes.

11.0 REGULATORY OBLIGATIONS

11.1 Institutional Review Board

The study protocol, informed consent/assent form, Investigator's Brochure, or package insert (as applicable), and any specific advertising will be submitted to, and approved by, an Institutional Review Board (IRB) before the start of the study. A form must be signed by the chairman or designee of the IRB noting the approvals. This notification of the board's approval along with a description by profession and gender of the board's composition will be provided to the Sponsor.

11.2 Study Documentation

This study will be conducted in compliance with the protocol, Good Clinical Practices (GCPs) and all applicable regulations, including the Federal Food, Drug and Cosmetics Act, US applicable Code of Federal Regulations (title 21), parts 50, 56, 312, 320 and any IRB requirements relative to clinical studies and the Declaration of Helsinki, June 1964, as modified by the 64th World Medical Association General Assembly, October 2013.¹⁷⁻²⁰

The Investigator will permit trial-related monitoring, audits, IRB review and regulatory inspections providing direct access to source data/documents.

11.2.1 Protocol

The Investigator indicated on FDA Form 1572 will act as the Principal Investigator at each study site. Protocols will be noted as approved by placement of the Novum Representative's signature

CONFIDENTIAL PROTOCOL

An Open Label, Safety Study to Assess the Potential for Adrenal Suppression Following Maximal Use Treatment with Desoximetasone 0.25% shampoo(Taro Pharmaceuticals U.S.A., Inc.) in Patients with Scalp Psoriasis

on the cover page. The Sponsor of the study will also approve the protocol by having a study-responsible individual sign the protocol cover page.

11.2.2 Informed Consent

An Informed Consent Form (ICF) that includes all of the relevant elements currently required by FDA and local State regulations will be provided to each prospective study patient before enrollment into the study. The type and method of study, tests to be administered, any potential or possible hazards, and the patient's right to withdraw from the study at any time will be explained to the patients by the Investigator or designee. Once the Investigator or designee is assured that an individual candidate understands the implications of participating in this study, the patient will be asked to give consent by signing and dating in the appropriate areas of the ICF. The Investigator or designee will also sign and date the form, along with a staff member who will sign the ICF as a witness to verify that the patient has indeed received information. For illiterate patients, verbal consent should be obtained in the presence of and be countersigned by a literate witness. If any other language is required, translation will be performed by a certified translator. A copy of the ICF will be provided to the patient.

11.2.3 Protocol and Informed Consent Changes

Revisions to the original protocol will be documented in amendments, incorporated as a preface to the new version and approved by the IRB. Any revision that substantially alters the study design or increases potential risk to the patient requires the patient's consent to continue in the study. Revisions to the original ICF will also be approved by the IRB. The approvals will be processed in accordance with the established IRB procedures. Copies of all protocol and ICF amendments/revisions, along with letters noting IRB approval, will be submitted to the Sponsor.

11.2.4 Source Documents and Case Report Forms

All patients will be identified by initials, date of birth, and a unique patient number. Source documents will be used to record all study-related data. Source document entries will be used to complete Case Report Forms (CRFs). A set of CRFs will be completed for each patient enrolled in the study. All data and CRFs will be reviewed, evaluated and signed by the Investigator, as required.

The original source documents and a copy of the corresponding CRFs will be retained by the Investigator. Patients who terminate early from the study will have the end of study (Visit 3) source/CRF completed.

11.2.5 Drug Accountability

All drug receipt, inventory, dispensing, dosing and reconciliation records will be maintained in compliance with Federal Regulations. The study drug will be dispensed to qualified study patients according to established procedures. At the end of the study (after the database has been locked) all used and unused study drug will be returned to Novum.

11.2.6 Drug Storage

All study product will be stored at controlled room temperature 15-30°C (59-86°F), in a secure place with access by authorized individuals only. The Investigator will be responsible for

CONFIDENTIAL PROTOCOL

An Open Label, Safety Study to Assess the Potential for Adrenal Suppression Following Maximal Use Treatment with Desoximetasone 0.25% shampoo(Taro Pharmaceuticals U.S.A., Inc.) in Patients with Scalp Psoriasis

maintaining accurate records of product receipt, dispensing, and return. At the end of the study, all study product will be returned to Novum.

11.2.7 Pregnancies

Patients with a positive pregnancy test during screening will not be enrolled in the study. Patients who report that they have become pregnant during the study or have a positive pregnancy test at any clinic visit will be followed to completion of the pregnancy. The pregnancy will be reported as an AE.

Female patients of childbearing potential must have been using and must agree to continue to use accepted methods of birth control, throughout the study. All female patients are considered to be of childbearing potential unless they are premenarchal, have been surgically sterilized or have been postmenopausal for at least 1 year. Abstinence is an accepted method of birth control. Alternatively, any of the following methods of birth control are acceptable: oral contraceptives, contraceptive patches/implants (e.g., Norplant[®]), Depo-Provera[®], double barrier methods (e.g., condom and spermicide) or IUD. Prior to study enrollment women of childbearing potential must be advised of the importance of avoiding pregnancy during study participation.

A negative result of a urine pregnancy test having a minimum sensitivity of at least 25 mIU/ml for hCG should be obtained, prior to study participation. Pregnancy testing will be performed at Visits 1, 2 and 3 and the results of all pregnancy tests (positive or negative) will be documented.

If following initiation of study treatment, it is subsequently discovered that a study patient is pregnant or may have been pregnant at the time of Investigational Product exposure, the Investigational Product will be permanently discontinued. The Principal Investigator must immediately notify the Medical Monitor of this event. Reporting timelines and Novum/Sponsor contact will be consistent with SAE reporting guidelines (see section 9.8.2 of the protocol), i.e., pregnancies will be reported to the Sponsor/Novum within 24 hours to the contacts listed in section 9.8.2.

Protocol-required procedures for study discontinuation and follow-up must be performed on the patient. Other appropriate pregnancy follow-up procedures should be considered if indicated. In addition, the Principal Investigator must report to the sponsor follow-up information regarding the course of the pregnancy, including perinatal and neonatal outcome. Infants should be followed for a minimum of eight weeks after birth.

11.2.8 Reporting Safety Information to the IRB

The Investigator must promptly report to the Investigator's IRB all unanticipated problems involving risks to patients. This includes death from any cause and all serious adverse events occurring during the study, regardless of the assessed causality.

11.2.9 Record Retention

All drug accountability records, CRFs, source data and related regulatory documents must be retained for at least ten years following completion of the study or for two years after the test product has been approved for marketing by the Food and Drug Administration.

CONFIDENTIAL PROTOCOL

An Open Label, Safety Study to Assess the Potential for Adrenal Suppression Following Maximal Use Treatment with Desoximetasone 0.25% shampoo(Taro Pharmaceuticals U.S.A., Inc.) in Patients with Scalp Psoriasis

11.2.10 Study Monitoring and Auditing

Novum will be responsible for monitoring the study according to Good Clinical Practice and applicable regulations. Monitoring visits are for the purpose of confirming adherence to the protocol and to verify complete and accurate data collection. The clinical site will make all records associated with the study available to Novum's representative during such visits and audits

The study may be subject to audit by the Sponsor, Sponsor Representative or by regulatory authorities. If such an audit occurs the Investigator must agree to allow access to required patient records. By signing this protocol, the Investigator grants permission to personnel from the Sponsor, its representatives and appropriate regulatory authorities for on-site monitoring of all appropriate study documentation, as well as on-site review of study procedures.

11.2.11 End of the Trial

The end of the trial is defined as the time at which the last patient has completed their last visit in the study. Upon completion of the study, the study drug will no longer be available to the patient but the Investigator can, at their discretion, discuss alternative treatments with the patient.

11.2.12 Clinical Study Report

At the end of the study a full report in e-CTD format will be prepared that will include a narrative of the clinical conduct and results of the study, a statistical report including a description of the analysis performed, and other documentation as may be appropriate.

CONFIDENTIAL PROTOCOL

An Open Label, Safety Study to Assess the Potential for Adrenal Suppression Following Maximal Use Treatment with Desoximetasone 0.25% shampoo(Taro Pharmaceuticals U.S.A., Inc.) in Patients with Scalp Psoriasis

13.0 APPENDICES**13.1 APPENDIX A****Investigator Global Assessment (IGA)**

To be eligible for inclusion in the study the IGA must be 3 or 4 at baseline. Patients will be considered to have shown improvement in disease severity if the IGA score decreases by at least one unit from the baseline score, and will be considered a treatment success if the IGA score decreases at least 2 units from the baseline score.

Score	Category	Description
0	Clear	Plaque elevation: no evidence of plaque elevation above normal skin level Scaling: no evidence of scaling Erythema: no redness
1	Minimal	Plaque elevation: very slight elevation above normal skin level, easier felt than seen Scaling: limited amount of very fine scales partially covers some of the plaques Erythema: very few of the plaques are light red
2	Mild	Plaque elevation: slight but definite elevation above the normal skin level, typically with edges that are indistinct or sloped on some of the plaques Scaling: mainly fine scales, some plaques are partially covered Erythema: some plaques are light red
3	Moderate	Plaque elevation: moderate elevation with rounded or sloped edges on most of the plaques Scaling: somewhat coarser scales; most plaques are partially covered Erythema: most plaques are red
4	Severe	Plaque elevation: marked to very marked elevation, with hard to very hard sharp edges on virtually all or all of the plaques Scaling: coarse, thick scales; virtually all or all plaques are covered; rough surface Erythema: virtually all or all plaques are bright to dusky red

[figure not shown]
CONFIDENTIAL PROTOCOL

An Open Label, Safety Study to Assess the Potential for Adrenal Suppression Following Maximal Use Treatment with Desoximetasone 0.25% shampoo(Taro Pharmaceuticals U.S.A., Inc.) in Patients with Scalp Psoriasis

13.2 APPENDIX B

Percent Scalp Affected

Investigators will use the following chart to identify areas and estimate scalp surface area affected by psoriasis plaques.¹⁶

Olsen/Canfield

CONFIDENTIAL PROTOCOL

An Open Label, Safety Study to Assess the Potential for Adrenal Suppression Following Maximal Use Treatment with Desoximetasone 0.25% shampoo(Taro Pharmaceuticals U.S.A., Inc.) in Patients with Scalp Psoriasis

13.3 APPENDIX C

Ocular Discomfort Assessment

At Visits 2 and 3 the patient will be asked to assess if any ocular discomfort was experienced, YES or NO, since the last clinic visit.

If YES is reported, the patient will be asked to report the signs and symptoms that apply from the list below or indicate any OTHER signs and symptoms experienced:

Redness	Stinging
Itching	Blur (decrease in vision)
Pain	Increased sensitivity
Swelling	Watery eyes
Burning	Spots, flashes and floaters
Eye Discharge	Foreign body sensation

In addition, the patient will be asked to indicate if the shampoo came into contact with their eye, YES or NO, since the last clinic visit. If YES is reported, the patient will be asked to rate the discomfort at the time of contact as None, Mild, Moderate or Severe.

CONFIDENTIAL PROTOCOL

An Open Label, Safety Study to Assess the Potential for Adrenal Suppression Following Maximal Use Treatment with Desoximetasone 0.25% shampoo(Taro Pharmaceuticals U.S.A., Inc.) in Patients with Scalp Psoriasis

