9.7.1 Adverse Event Definitions

Adverse Event: Any untoward medical occurrence in a patient or clinical investigation patient administered a pharmaceutical product and which does not necessarily have a causal relationship with treatment. An AE can therefore be any unfavorable and unintended sign, symptom, or

CONFIDENTIAL PROTOCOL

An Open Label, Safety Study to Assess the Potential for Adrenal Suppression Following Maximal Use Treatment with Desoximetasone 0.25% shampoo(Taro Pharmaceuticals U.S.A., Inc.) in Patients with Scalp Psoriasis

disease, temporally associated with the use of a medicinal (investigational) product, whether or not related to this product. This includes events not seen at baseline, or worsened even if present at baseline.

Unexpected Adverse Event: An adverse event where the nature or severity of is not consistent with the applicable product information (e.g., Investigator's Brochure for an unapproved investigational product or package insert/summary of product characteristics for an approved product).

Adverse Drug Reaction: All noxious and unintended responses to a medical product related to any dose should be considered adverse drug reactions. The response to a 'medical product' means that a causal relationship between a medicinal product and an adverse event is at least a reasonable possibility, i.e., the relationship cannot be ruled out.

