**L16.2.8.6 Listing of Ocular Signs/Symptoms Assessment**

---

| Patient Number | Visit | Did the patient experience any ocular discomfort ? | Signs/Symptoms the patient experienced | Did the shampoo come into contact with the patient's eyes? | Patient's overall discomfort |
|----------------|-------|----------------------------------------------------|----------------------------------------|------------------------------------------------------------|------------------------------|
| xx-xxxx        | 2     | Yes                                                | Redness/Pain                           | Yes                                                        | Mild                         |
|                | 3     | No                                                 |                                        |                                                            |                              |
| xx-xxxx        | 2     | Yes                                                | Itching/Pain                           | Yes                                                        | None                         |
|                | 3     | Yes                                                | Itching/Pain                           | No                                                         |                              |

---

Created on: ddmmmyy hh:mm

Page 1 of N

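### The patient-reported ocular discomfort item has no matching Visit 1 answer and is rated for severity only at reported shampoo contact, so the ocular listing alone cannot separate pre-existing from new or worse discomfort

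*Protocol*

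**What the plan says.** **Timing.** Protocol Appendix C sets the question for Visits 2 and 3: "the patient will be asked to assess if any ocular discomfort was experienced, YES or NO, since the last clinic visit". SAP 6.3.4 and SAP Appendix C repeat this. The study schematic in both documents leaves the ocular assessment blank at Visit 1, and none of the sixteen steps in protocol 9.5.1 asks it.

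**Content.** After a YES, "the patient will be asked to report the signs and symptoms that apply from the list below or indicate any OTHER signs and symptoms experienced". The list includes redness, itching, watery eyes, blur and floaters. It asks for neither severity nor date of onset.

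**Severity.** A separate item asks about shampoo contact with the eye. Only a YES to that item leads to a rating: "the patient will be asked to rate the discomfort at the time of contact as None, Mild, Moderate or Severe".

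**Reporting.** SAP 6.3.4 plans a by-patient, by-visit listing and no ocular table. Shell L16.2.8.6 has one column asking "Did the shampoo come into contact with the patient's eyes" and a rating column headed "Patient's overall discomfort".

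**Adverse events.** Protocol 9.7.1 has a baseline rule: "This includes events not seen at baseline, or worsened even if present at baseline". Section 9.7.2 has the Investigator grade severity.

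**The concern.** Protocol 10.2 names ocular safety among the safety evaluations. There is no control arm, so a patient's own state before treatment is the natural comparison for a symptom report. The symptoms on the checklist are non-specific. Exclusion 15 removes glaucoma, posterior subcapsular cataracts and other eye conditions that the Investigator judges an undue risk, so a patient with ordinary dry or allergic eyes may be enrolled. That patient could truthfully answer YES at both later visits, and the ocular listing would show two on-treatment entries with nothing before them.

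A second gap is severity. Discomfort that the patient does not connect with shampoo contact gets symptom names but no grade. Where a rating does exist, the SAP column heading makes a momentary rating look like a rating of the whole interval.

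**Working it through.** The plan states no ocular event rate, precision or power, so there is no figure to reproduce. The check is mainly of text, followed by a calculation for scale.

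**1. Is there a matched pre-dose value?** No. Appendix C, SAP 6.3.4, both schematics and 9.5.1 agree. By contrast, IGA, percent scalp affected, vital signs, the HEENT exam, laboratory tests and the cortisol test all have Visit 1 values. The recall intervals are about two weeks: nominally 14 − 1 = 13 days to Visit 2 and 29 − 14 = 15 days to Visit 3. A two-week look-back at Visit 1 would therefore be comparable.

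**2. When is severity recorded on this form?**

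| Discomfort since last visit | Contact reported | Symptoms | Patient-rated severity |
|---|---|---|---|
| Yes | Yes | Listed | At time of contact only |
| Yes | No | Listed | None collected |
| No | Yes | Not asked | At time of contact only |
| No | No | Not asked | Not applicable |

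No combination gives a severity for the discomfort over the interval. Shell L16.2.8.6 agrees: its sample row with discomfort Yes, itching and pain, and contact No has an empty rating.

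**3. Does the SAP heading match the item?** No. One sample row shows discomfort Yes, itching and pain, contact Yes, and a rating of None. Under Appendix C this is coherent: the patient had discomfort in the interval but none at the moment of contact. Under the SAP heading the row contradicts itself.

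**4. Do other records fill the gap?** In part.

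- Visit 1 medical history covers acute and chronic conditions. Listing L16.2.4.2 carries start date, end date and an ongoing flag.
- Medication use over 12 weeks is recorded, with dates and indication in L16.2.4.3.
- A HEENT exam is done at Visit 1. It is a clinician's examination, not the patient's answer to the same question.
- An eye complaint entered as an adverse event is judged against baseline (9.7.1), graded by the Investigator (9.7.2) and dated in L16.2.7. No section says when an ocular YES is entered as one.

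**5. Scale, on an assumption.** Let b be the share of patients with an eye symptom at entry that persists on study. The documents give no value for b. The expected number of YES patients from this source is n × b, and the chance of at least one is 1 − (1 − b)^n. The enrolment ceiling is n = 40 and the evaluable target is n = 20.

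| b | n = 20: expected | n = 20: at least one | n = 40: expected | n = 40: at least one |
|---|---|---|---|---|
| 5% | 20 × 0.05 = 1 | 1 − 0.95^20 = 64% | 40 × 0.05 = 2 | 1 − 0.95^40 = 87% |
| 10% | 20 × 0.10 = 2 | 1 − 0.90^20 = 88% | 40 × 0.10 = 4 | 1 − 0.90^40 = 99% |
| 20% | 20 × 0.20 = 4 | 1 − 0.80^20 = 99% | 40 × 0.20 = 8 | 1 − 0.80^40 > 99% |

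The ocular listing alone could not tell these answers from new discomfort.

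**The case against.** The strongest reply is that a baseline exists even though it is not item-matched. History, medication records and the HEENT exam are all taken at Visit 1, and exclusions 15 to 17 remove some eye disease, recent eye surgery and infection of the head and neck. Patients are also asked about adverse events at Visits 2 and 3, so an eye complaint can be dated and graded whether or not shampoo touched the eye. The SAP calculates no ocular rate, so no estimate is biased. SAP section 7 says that table headers will be adjusted as needed, and SAP Appendix C carries the correct wording for the contact rating.

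Much of this stands, and it rules out several stronger readings that a reader might infer:

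- *That the Visit 1 answer would be the only reference.* It would be the only like-for-like one; the other Visit 1 records give partial information.
- *That the questionnaire decides who gets an ocular evaluation.* Protocol 9.6.9 leaves this to the Investigator, who weighs HEENT findings together with what the patient reports.
- *That ungraded discomfort has no severity anywhere in the trial.* This is true of the questionnaire and its listing, not of a complaint recorded as an adverse event.
- *That the final listing will misreport the rating.* The shell is illustrative and the CRF is not among the documents. What is established is a mismatch to correct.

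The reply does not supply a matched patient-reported baseline, a severity item for discomfort without contact, or a rule linking a YES to the adverse event record.

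**Conclusion.** The point holds as a cheap improvement to a secondary safety measure. The questionnaire and its listing alone cannot separate pre-existing from new or worsened ocular discomfort, and they carry no patient-rated severity when contact is not reported. The SAP heading for the contact rating does not match the item. The HPA axis endpoint is not affected.

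The size is uncertain. The 2–8 of 40 (1–4 of 20) rests on an assumed 5–20% of patients with symptoms present at entry that persist. A reader might stretch it to all eye symptoms unrelated to the drug. That would go too far, because symptoms that first arise during the study would still be new relative to Visit 1, and a single-arm trial cannot attribute them.

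**What to change.** - **Protocol Appendix C and schematic (with the SAP copies):** ask the same YES/NO question and symptom list at Visit 1, before the first dose, for the previous 2 weeks. Ask the None-to-Severe rating whenever discomfort is YES, at every visit, and keep the contact rating as a separate item.
- **SAP L16.2.8.6:** add the Visit 1 row, relabel the existing column as discomfort at time of contact, and add a column for the new rating.
- **SAP 6.3.4:** count patients whose discomfort is new or worse than at Visit 1.
- **Two clarifications:** state when an ocular YES is carried into the adverse event record (the rule is for the sponsor to set), and correct protocol 9.6.9, which sends the reader to Appendix D, the cortisol test, for this assessment.

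The cost is a few CRF items at visits already held, about a minute per patient, a CRF version change, a shell edit and one count. If data collection has finished, the column can still be relabelled at almost no cost.
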